11.1 Risk Assessment

A trial-specific risk assessment will be performed by the Sponsor, in collaboration with the Chief Investigator and the PI prior to the start of the trial.

The three parties above will perform a risk assessment to assess the risks and benefits of trial participation to individual participant safety, as well as the risks that underlie the validity of the trial results with respect to safety and immunogenicity outcome measurements.

This assessment will be used to guide the development of procedures with respect to informed consent, confidentiality, trial monitoring and audit, and lead to the development of a Data Management Plan (DMP) and Safety Reporting Plan and Monitoring Plan. This risk assessment will be updated as required during the course of the trial.

11.1.1 SAFETY AND RIGHTS OF PARTCIPANTS

The pre-clinical data available for LNP-MARVsaRNA, LNP-EBOVsaRNA and LNP-LASSAsaRNA for four species (mice, guinea pigs, rats and pigs) suggest that this product will be similar to licensed RNA vaccines and cause mild-moderate reactions that are transient. However, this is a first-in-human trial and therefore there will be a sentinel cohort with one individual allocated to each group. There will be immediate review of notable and serious adverse events with onward reporting to the TSC, and clear indications for pausing injections in individuals and the trial.

It will be necessary to hold personal contact details in order to collect the data on reactogenicity. The justification for this will be explained in the PIS as well as the storage and destruction of these data after the trial.

11.1.2 PROJECT DESIGN AND RELIABILITY

There is considerable interest in participating, and retention in previous early phase studies at the CRF has always been good. For the purposes of reporting, immune responses will be assessed in a single laboratory, although samples are likely to be analysed in other laboratories too. They will be couriered using a reliable courier.

11.1.3 PROJECT MANAGEMENT AND GOVERNANCE

Imperial College London has worked with the Clinical Research Facility at Chealsea and Westminster hospital on different trials including vaccines 2 previous clinical trials.

11.2 Monitoring

The Clinical Trial manager will review electronic data for errors and missing data points.

Other essential trial issues, events and outputs will be detailed in the Monitoring Plan that is based on the trial-specific Risk Assessment.

The trial will be monitored periodically by the Sponsor (Research Governance and Integrity Team (RGIT)), according to the monitoring plan, to assess the progress of the trial, verify adherence to the protocol, ICH GCP E6 guidelines and other national/international requirements and to review the completeness, accuracy and consistency of the data.

Monitoring procedures and requirements will be documented in a Monitoring Plan, developed in accordance with the risk assessment.

11.3 On-site and Remote Monitoring

The frequency, type and intensity for routine monitoring and the requirements for triggered monitoring will be detailed in the Monitoring Plan. This plan will also detail the procedures for review and sign-off. Remote or self-monitoring will be utilised through the course of the trial. Site staff may be asked to scan and send anonymised sections of a participant's medical record or in the case of consent forms remote review by videoconferencing

or transfer via secure portals may be utilised to enable complete remote verification. Site staff may also be asked to complete a form to confirm compliance with protocol procedures.

11.3.1 DIRECT ACCESS TO PARTICIPANT RECORDS

Participating investigators should agree to allow trial-related monitoring, including audits, ethics committee review and regulatory inspections by providing direct access to source data and documents as required. Participants' consent for this must be obtained.

11.3.2 CONFIDENTIALITY

Investigator site, and Sponsor must follow the principles of the UK Data Protection Act.

All personal data leaving the investigator site will be pseudonymised in that it will bear the participants' trial ID and not readily identifiable information such as name or contact details. The investigator site will maintain a participant identification list which links trial IDs to participants' names and NHS numbers (NHS sites only).

The exceptions to the above are:

Details such as first name, telephone number and email address will be entered by investigator site
staff into the EDC system, so that the system can communicate directly with participants, to send
reminder messages for example. These details will be encrypted and stored in the EDC system such
that only the relevant investigator site staff can view them. Sponsor will be unable to view them.

12. REGULATORY & ETHICAL ISSUE

12.1 Clinical Trials Authorisation

This trial has CTA from the UK Competent Authority; MHRA. Reference: xxx

12.1.1 REGULATORY COMPLIANCE

The trial will be conducted in compliance with the approved protocol, the Declaration of Helsinki 1996, the principles of Good Clinical Practice (GCP) as laid down by the ICH topic E6 (R2), Commission Clinical Trials Directive 2005/28/EC* with the implementation in national legislation in the UK by Statutory Instrument 2004/1031 and subsequent amendments, General Data Protection Regulation and the UK Data Protection Act 2018, and the UK Policy Framework for Health and Social Care Research.

*Until the Clinical Trials Regulation EU No 536/2014 becomes applicable, the trial will be conducted in accordance with the Clinical Trials Directive as implemented in the UK statutory instrument. When the directive is repealed on the day of entry into application of the Clinical Trial Regulation the trial will work towards implementation of the Regulation (536/2014) following any transition period.

12.1.2 DATA COLLECTION & RETENTION

Worksheets, clinical notes and administrative documentation should be kept in a secure location (for example, locked filing cabinets in a room with restricted access) and held for a minimum of 10 years after the end of the trial. During this period, all data should be accessible, with suitable notice, to the competent or equivalent authorities, the Sponsor, and other relevant parties in accordance with the applicable regulations. The data may be subject to an audit by the competent authorities. Medical files of trial participants should be retained in accordance with the maximum period of time permitted by the hospital, institution or private practice.

12.2 Ethical Approval and Conduct

The Study Coordination Centre has obtained approval from the xxx Research Ethics Committee (REC) and Health Research Authority (HRA). The trial will also receive confirmation of capacity and capability from the participating NHS Trust before accepting participants into the trial or any research activity is carried out. The trial will be conducted in accordance with the recommendations for physicians involved in research on human subjects as detailed under Section 12.1.1 above.

12.2.1 ETHICAL CONSIDERATIONS

Please see Section 8.1 for the risks identified for the safety and rights of participants, which include the risk of unexpected serious adverse reactions and the need to collect and hold personal data. The main ethical considerations, and mitigations, are described below:

• The trial is in healthy volunteers, so all visits required by the trial are in addition to their usual lifestyle and therefore are a burden. Vaccine trials are (necessarily) relatively lengthy, so participation

- represents a significant time commitment. The requirement to attend all trial visits within specified windows might be an inconvenience to some volunteers if their circumstances change during the trial.
- Fainting may occur around the time of vaccine injection or blood sampling, particularly in those who
 strongly dislike needles. To minimise this risk, participants will be asked to recline or lie down during
 those procedures.
- Blood tests can sometimes cause bruising and soreness of the arms or, very rarely, a blockage of a vein or a small nerve injury which can cause numbness and pain.
- The vaccine has not been tested for safety in pregnancy and might harm an unborn child. The
 contraception requirements for women participants of child-bearing potential might be a burden. Male
 participants will also be required to use contraception with female partners capable of becoming
 pregnant.
- The collection of sensitive or personal data will be undertaken only by staff trained in GCP and in the trial protocol.
- Participants will be informed of the results either at a seminar, or by email or on the phone. The PIS
 explains the hope to publish the results in medical journals, and present them at international
 conferences, and clarifies that participants will not be named in any of these or identified in any other
 way.
- Participants might believe that they are entitled to a share of potential future profits from commercialisation of the vaccine. The PIS explains that this is not the case.
- The confidentiality of participants' personal information is described in Section 12.4.
- The trial has some medication restrictions: non-trial vaccines received within 28 days before or after
 any trial vaccination are not allowed; systemic immunosuppressive agents, such as a corticosteroid,
 may not be administered during the trial; dermal steroids are allowed but not if applied to the IM
 injection site.
- Based on other vaccines against different diseases, including those that use synthetic mRNA, the side
 effects are expected to be mild to moderate, short-lived reactions at the injection site such as
 discomfort, warmth, redness and swelling. Short-lived systemic symptoms such as fatigue, general
 malaise and headache are expected very commonly (more than 1 in 10 people). Less common reactions
 (expected in fewer than 1 in 10 people, but in more than 1 in 100) include chills, muscle pain, rash, and
 injection site itching.
- Uncommon side effects (1 in 100 people) include abdominal pain, diarrhoea, sore throat, enlarged lymph nodes, insomnia and allergic reactions such as rash or itching. These are also anticipated to resolve within a few days (<7 days).
- Rare reactions associated with mRNA vaccine, that may also be associated with saRNA vaccines include
 (less than 1 in 1,000 people, but more than 1 in 10,000) enlarged lymph nodes, high fever (≥40 °C),
 hypersensitivity (exaggerated reaction to the vaccine), urticaria (raised, itchy skin rash), and granuloma
 (area of inflammation in the skin) or sterile abscess (lump) at the injection site. Non-severe allergic
 reactions (1 in 1,000) such as hives or swelling of the face may occur and severe very rare allergic

reactions (1 in 1 million) may occur, however those with a history of allergy will not be eligible. Very rarely (less than 1 in 10,000 people) vaccines may cause convulsions with fever, drowsiness, and macrophagic myofasciitis (a rare muscle disease).

Myocarditis (inflammation of the heart muscle), and Pericarditis (inflammation of the lining outside the
heart) are also very rare potential serious side effects associated with mRNA vaccine occurring most
commonly in adolescent males 12 through 17 years of age (1 in 37,000). Those with any previous history
of either of these conditions will not be eligible. These risks will be carefully explained so that
participants know what is involved and what to expect in the way of side effects.

These risks will be carefully explained so that participants know what is involved and what to expect in the way of side effects.

Participants will be monitored closely during the trial, to identify as early as possible any problems so that they can be handled appropriately. They will be given 24-hour phone numbers in case they wish to speak to a doctor.

Because this is a first-in-human trial, there will be sentinel participants in each dose group, who will be vaccinated 2 days before any others. The dose evaluation plan is detailed in **Section 4.1.1**.

The rules for pausing and discontinuing vaccinations in individuals and all participants in the trial have been clearly defined.

Participants will be paid for their time, inconvenience and travel expenses: £200 per scheduled visit, paid as a lump sum at the end of participation. This includes any travel expenses they might incur. Volunteers who attend screening but who are not enrolled will not receive payment. If their participation ends early, participants will be paid for the number of visits they've attended.

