8.1.2 EXPECTED ADVERSE EVENTS

The safety and reactogenicity of the IMP is expected to be comparable to the safety observed in previous clinical trials conducted where saRNA have been tested with other vaccine antigens in Phase I clinical trials (COVAC1, COVAC Uganda). See summary table 5 below for systemic and local reactions reported in individuals who received a 5 µg dose of LNP-nCoVsaRNA vaccine.

Up to 100% of participants are expected to experience grade 1-2 systemic reactions including fatigue, myalgia, headaches, chills/shivering and arthralgia. Similarly, close to 100% of participants are expected to experience grade 1-2 local reactions, with pain and tenderness/discomfort likely to be the most common local reactions.

Uncommon reactions include high temperature (≥ 38°C), nausea and vomiting, and erythema and induration at site of injection.

Vasovagal syncope (i.e. fainting), may occur in this population of subjects. It will be attempted to minimise the occurrence of this reaction, by allowing the subjects to lie down during administration of vaccine and blood drawings.

Table 5. Adverse Events in participants the COVAC1 clinical trial who received a 5 μg dose of LNP-nCoV-saRNA

		LNP-nCoVsaRNA dose
		5.0 μg N=24
	Any	
	Normal	0 (0.0%)
	Grade 1	8 (33.3%)
	Grade 2	14 (58.3%)
	Grade 3	2 (8.3%)
	Temperature	
	Normal	21 (87.5%)
	Grade 1	2 (8.3%)
	Grade 2	0 (0.0%)
	Grade 3	1 (4.2%)
	Chills/shivering	
	Normal	10 (41.7%)
	Grade 1	11 (45.8%)
	Grade 2	3 (12.5%)
	Myalgia (flu-like general ı	
	Normal	5 (20.8%)
	Grade 1	13 (54.2%)
	Grade 2	6 (25.0%)
	Grade 3	0 (0.0%)
	Arthralgia	
0	Normal	11 (45.8%)
Systemic	Grade 1	9 (37.5%)
	Grade 2	4 (16.7%)
	Grade 3	0 (0.0%)
	Fatigue	
	Normal	3 (12.5%)
	Grade 1	11 (45.8%)
	Grade 2	10 (41.7%)
	Grade 3	0 (0.0%)
	Sidd 0	0 (0.070)
	Headache Normal	2 (9 20/)
	Grade 1	2 (8.3%) 14 (58.3%)
	Grade 2	8 (33.3%)
	Nausea Normal	19 (79.2%)
	Grade 1	5 (20.8%)
	Grade 2	0 (0.0%)
	Grade 3	0 (0.0%)
		(())
	Vomiting	
	Normal	24 (100.0%)
		24 (100.0%) 0 (0.0%)
	Normal Grade 3	0 (0.0%)
	Normal Grade 3 Any Normal	0 (0.0%)
	Normal Grade 3 Any Normal Grade 1	0 (0.0%) 1 (4.2%) 15 (62.5%)
	Normal Grade 3 Any Normal	0 (0.0%)
	Normal Grade 3 Any Normal Grade 1	0 (0.0%) 1 (4.2%) 15 (62.5%)
	Normal Grade 3 Any Normal Grade 1 Grade 2	0 (0.0%) 1 (4.2%) 15 (62.5%) 8 (33.3%)
	Normal Grade 3 Any Normal Grade 1 Grade 2	0 (0.0%) 1 (4.2%) 15 (62.5%)
	Normal Grade 3 Any Normal Grade 1 Grade 2 Pain Normal	0 (0.0%) 1 (4.2%) 15 (62.5%) 8 (33.3%)

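### Section 12.2.1 puts chills and muscle pain at fewer than 1 in 10 people, but Section 8.1.2 and Table 5 of the same protocol point to 58% and 79%

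*Protocol*

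**What the plan says.** All references are to the protocol.

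- **Section 12.2.1** grades expected side effects by frequency. Fatigue, malaise and headache are placed above 1 in 10. The next band down is "expected in fewer than 1 in 10 people, but in more than 1 in 100) include chills, muscle pain, rash". The stated basis is "Based on other vaccines against different diseases, including those that use synthetic mRNA". The section then says: "These risks will be carefully explained so that participants know what is involved".
- **Section 8.1.2** states that "The safety and reactogenicity of the IMP is expected to be comparable to the safety observed in previous clinical trials" of saRNA with other antigens, and continues: "Up to 100% of participants are expected to experience grade 1-2 systemic reactions including fatigue, myalgia, headaches, chills/shivering and arthralgia".
- **Table 5**, in Section 8.1.2, tabulates reactions by grade in 24 recipients of 5 µg of the earlier COVID-19 saRNA vaccine.
- **Section 8.1.2** also lists as uncommon, without giving that word a number, high temperature together with "nausea and vomiting, and erythema and induration at site of injection".
- **Section 3.2.3**, which largely parallels the side-effect text of Section 12.2.1, lacks the sentence with the band below 1 in 10. It does not mention chills or muscle pain at all.

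**The concern.** One document gives two incompatible frequencies for the same two symptoms. Chills and myalgia are not incidental: both are solicited systemic reactions and so named outcome measures (Sections 4.2 and 10.2).

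The lower frequency stands in the section that describes what participants will be told. They are healthy volunteers in a first-in-human trial whose only prospect of benefit the protocol calls theoretical (Section 3.3). If the consent discussion follows Section 12.2.1, a volunteer would hear that fewer than 1 in 10 people get chills or muscle pain. The data that the protocol takes as its guide show that most recipients had them.

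**Working it through.** **Inputs, from Table 5 (N=24, 5 µg)**

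| Symptom | None | Grade 1 | Grade 2 | Grade 3 | Row sum |
|---|---|---|---|---|---|
| Chills/shivering | 10 | 11 | 3 | no row | 24 |
| Myalgia | 5 | 13 | 6 | 0 | 24 |
| Nausea | 19 | 5 | 0 | 0 | 24 |

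The printed percentages reproduce. For chills, 10/24 = 41.7%, 11/24 = 45.8% and 3/24 = 12.5%. For myalgia, 5/24 = 20.8%, 13/24 = 54.2% and 6/24 = 25.0%.

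**Any-grade rate = (24 − none)/24**

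- Chills: (11 + 3)/24 = 14/24 = 58.3%
- Myalgia: (13 + 6)/24 = 19/24 = 79.2%

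**Ratio to the top of the stated band (10%)**

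- Chills: 58.3/10 = 5.8
- Myalgia: 79.2/10 = 7.9

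Because 10% is the most favourable reading of a band that runs from 1% to 10%, these are the smallest ratios that the point estimates allow.

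**Uncertainty.** Wilson 95% interval: [p + z²/(2n) ± z·√(p(1−p)/n + z²/(4n²))] / (1 + z²/n), with z = 1.96 and n = 24.

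- Chills: centre 0.572, half-width 0.183, giving 38.8% to 75.5%
- Myalgia: centre 0.751, half-width 0.156, giving 59.5% to 90.8%

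The exact (Clopper-Pearson) lower limits are 36.6% and 57.8%, which still give ratios of about 3.7 and 5.8.

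**Could a true rate of 10% have produced these counts?** With X ~ Binomial(24, 0.10), P(X ≥ 14) = 7 × 10⁻⁹ and P(X ≥ 19) = 3 × 10⁻¹⁵. Sampling variation is not an explanation.

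**Do mild cases account for the gap?** With Grade 1 excluded, chills is 3/24 = 12.5% and myalgia 6/24 = 25.0%. Both point estimates remain above 10%.

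**Minor point, nausea.** 5/24 = 20.8% (Wilson 9.2% to 40.5%), in a sentence that calls it uncommon.

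**The case against.** **Different sources.** The best defence is that Section 12.2.1 draws on vaccines in general, whereas Table 5 reports one saRNA vaccine with a different antigen, so the two need not agree. The difference in source is real but does not remove the conflict. Section 8.1.2 adopts the saRNA experience as the expectation for these products and names both symptoms. Section 12.2.1 itself opens by referring the reader to Section 8.1 for the risks. That cross-reference may be misdirected, since its wording resembles the heading of Section 11.1.1, but the conflict does not depend on it.

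**Small sample.** Table 5 has 24 participants, so the size of the gap is uncertain. Its direction is not.

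A reader might also infer more than the documents support:

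- *That the whole risk statement is 6 to 8 times too low.* It is not. Fatigue, malaise and headache are placed above 1 in 10, which agrees with Table 5 for fatigue and headache.
- *That volunteers are being misinformed.* The participant information is not available here, so this cannot be checked. The lay summary mentions chills and temperature without a low frequency.
- *That ordinary reactions would be mistaken for a safety signal.* Expectedness is judged against the reference safety information in the Investigator's Brochure (Table 4 and Section 8.2.4). The pausing rules in Section 7.1.5 use grade, persistence, seriousness and counts. Neither uses the frequencies in Section 12.2.1.
- *That uncommon in Section 8.1.2 means about 1%.* The 1 in 100 figure belongs to other lists, in Sections 3.2.3 and 12.2.1. The same sentence also covers vomiting (0/24) and erythema (1/24), for which the word is reasonable. Raised temperature (3/24) is too imprecise, and its grade cut-offs are not printed.
- *That Table 5 gives an unusable Grade 3 rate.* Its overall systemic row shows 2/24 and the legible symptom rows show one Grade 3 event. A component that is not listed, or was lost when the table was extracted, would explain that. The table also does not say whether it covers one or both injections, so no pausing probability can be built on it.

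**Conclusion.** The concern holds for chills and muscle pain in Section 12.2.1. The stated band of 1% to 10% contradicts Section 8.1.2 and Table 5, where the rates are 58.3% and 79.2%. That is 5.8 and 7.9 times the ceiling as point estimates, and about 3.7 and 5.8 times at the exact lower 95% limits. On these data both symptoms belong in the section's own highest band.

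This rests on one assumption, which the protocol itself makes: that reactogenicity will be comparable to the earlier saRNA vaccine. Table 5 describes 5 µg. Groups 4 and 5 receive 9 and 13 µg in total, and Section 3.1.6.2 reports dose-dependent reactogenicity on this platform, so nothing in the protocol suggests lower rates in those groups.

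The error is an internal inconsistency in a stated risk. It should be corrected because the explanation to participants draws on it. It leaves the trial's endpoints, analyses and sample size untouched. The wording on nausea is a smaller inconsistency: the point estimate is 20.8%, but the interval reaches down to 9%.

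**What to change.** 1. In Section 12.2.1, move chills and muscle pain from the band below 1 in 10 to the band above 1 in 10. Cite Table 5, and note that it describes 5 µg while Groups 4 and 5 receive 9 and 13 µg in total.
2. In Section 3.2.3, add both symptoms to the corresponding band. Nothing needs replacing there, because the faulty sentence is absent.
3. Check that the participant information gives the same frequencies, and align it if it does not.
4. As a minor edit, reconcile the word uncommon for nausea in Section 8.1.2 with 5/24 in Table 5.

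The other listed frequencies should not be replaced wholesale from Table 5. It has no rows for rash, diarrhoea, lymph nodes, allergy or myocarditis, and 24 participants cannot inform bands of 1 in 1,000 or rarer.

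The cost is a wording change to the protocol and, if needed, to the participant materials. The stated tolerability becomes less favourable. No data collection or analysis changes.

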12.3 Consent

Consent to enter the trial must be sought from each participant only after a full explanation has been given, an information leaflet offered, and time allowed for consideration. Signed participant consent should be obtained. The right of the participant to refuse to participate without giving reasons must be respected. After the participant has entered the trial, the clinician remains free to give alternative treatment to that specified in the protocol at any stage if he/she feels it is in the participant's best interest, but the reasons for doing so should be recorded. In these cases, the participants remain within the trial for the purposes of follow-up and data analysis. All participants are free to withdraw at any time from the protocol treatment without giving reasons and without prejudicing further treatment.

12.4 Confidentiality

Data will be pseudonymised. Pseudonymised data is data that can be linked back to a person (e.g. coded data). It is considered both personal and identifiable data. Anonymised data is data that has no code and cannot be

linked back to a person (e.g. aggregated data for publication, data without a code that cannot be linked back to a person).

The Chief Investigator will preserve the confidentiality of participants taking part in the trial and is registered under the Data Protection Act.

